## **8.2 Subject demographics/other baseline characteristics**

Baseline CSU activity will be assessed using the eDiary from Day -7 to Day -1 of the day 1 visit of the treatment period. Subject demographic and baseline characteristic data including sex, race and ethnicity that was collected as a part of the core study will be used for this extension study. Relevant medical history (including evaluation of inclusion/exclusion criteria, CSU history and cardiovascular history) and current medical condition present before signing the informed consent will be captured. Where possible, diagnoses, and not symptoms, will be recorded. Data on subjects' family history of malignancies will be collected on the respective eCRF page, only when a subject has a malignancy event reported during the study, to assess possible risk factors related to any malignancies.

Country specific regulations should be considered for the collection of demographic and baseline characteristics in alignment with eCRF.

## **8.3 Efficacy**

All subjects will be provided with an electronic device (eDiary) that contains the following assessments: Urticaria Patient Daily Diary (UPDD), [REDACTED]

Site and subjects will receive appropriate training and guidance on the use of the eDiary and will receive clear instructions on the completion of the assessments. Investigators need to review the eDiary at every visit.

Assessments will be completed twice daily (UPDD), [REDACTED] or as detailed in the assessment schedule.

In general, subjects complete eDiary questionnaires at home and independent of study visits. Subjects will be instructed to complete eDiary entries after they took their study medication throughout the treatment period. [REDACTED]

Site personnel must allow subjects to complete the questionnaire on their own without any assistance from the site staff.

As per [Section 4.6](#), during a Public Health emergency as declared by Local or Regional authorities, i.e., pandemic, epidemic or natural disaster, that limits or prevents on-site study visits, Clinical Outcomes Assessment (COA) data may be collected remotely (e.g., via web portal) depending on local regulations, technical capabilities and following any applicable training in the required process.

### 8.3.1 eDiary assessments

#### 8.3.1.1 Urticaria Patient Daily Diary (UPDD)

UPDD includes Urticaria Activity Score (UAS) which assesses twice daily severity of itch and number of hives. [REDACTED] angioedema occurrence, its management and records the calls to an healthcare professional (HCP) ([Section 16.5](#)). The components are presented in [Table 8-3](#) and the relevant weekly scores are described below.

**Table 8-3 UPDD**

Diary component	When assessed
Urticaria Activity Score (UAS) • Itch severity • Number of hives	Morning & evening

[REDACTED]

##### 8.3.1.1.1 Weekly Hives Severity Score (HSS7)

The hives (wheals) severity score, defined by number of hives, will be recorded by the subject twice daily in their eDiary, on a scale of 0 (none) to 3 (> 12 hives/12 hours; [Table 8-4](#)). A weekly score (HSS7) is derived by adding up the average daily scores of the 7 days preceding the visit. The possible range of the weekly score is therefore 0 – 21.

[REDACTED]

**Table 8-4 Hives Severity Score**

Score	Hives (Wheals) (every 12 hours)
0	None
1	1-6 hives/12 hours
2	7-12/12 hours
3	> 12 hives/12 hours

#### 8.3.1.1.2 Weekly Itch Severity Score (ISS7)

[figure not shown]
The severity of the itch will be recorded by the subject twice daily in their eDiary, on a scale of 0 (none) to 3 (severe) (Table 8-5). A weekly score (ISS7) is derived by adding up the average daily scores of the 7 days preceding the visit. The possible range of the weekly score is therefore 0 - 21.

[figure not shown]
**Table 8-5 Itch Severity Score**

[figure not shown]
Score	Pruritus (Itch) (every 12 hours)
0	None
1	Mild (minimal awareness, easily tolerated)
2	Moderate (definite awareness, bothersome but tolerable)
3	Severe (difficult to tolerate)

#### 8.3.1.1.3 Weekly Urticaria Activity Score (UAS7)

The UAS7 is the sum of the HSS7 score and the ISS7 score. The possible range of the weekly UAS7 score is 0 – 42 (highest activity).

### **8.3.3 Appropriateness of efficacy assessments**

At the time the omalizumab studies were carried out, the treatment paradigm focused primarily on itch (ISS7) as a key symptom of CSU. Over the past several years the goal of therapy has evolved and the current target of therapy as described in the current CSU treatment guidelines ([Zuberbier et al. 2018](#)) is to treat the disease until it is gone, i.e. complete control of the disease (UAS7= 0).

### **8.4 Safety/Tolerability**

Safety assessments are specified below with the assessment schedule detailing when each assessment is to be performed.

For details on AE collection and reporting, refer to [Section 10](#), Safety monitoring and reporting.

Main safety and tolerability assessments include:

- AEs and SAEs, including AEs leading to treatment discontinuation and events of interest such as infections, bleeding/bruising, QT-prolongation and myelomodulating effects (i.e. cytopenias)
- Physical examination
- Vital signs
- Laboratory evaluations
- ECG

**Table 8-9 Physical Assessments**

Assessment	Specification
Physical examination	A complete physical examination (performed at enrollment, see Table 8-1 ) will include the examination of general appearance, skin, neck (including thyroid), eyes, ears, nose, throat, lungs, heart, abdomen, back, lymph nodes, extremities, vascular, and neurological. If indicated based on medical history and/or symptoms, rectal, external genitalia, breast, and pelvic exams will be performed.  A short physical exam (performed at visits indicated in Table 8-1 and Table 8-2 ) will include the examination of general appearance, assessment of the skin for sign of urticaria and other skin lesions, and vital signs (blood pressure [SBP and DBP] and pulse).  Information for all physical examinations must be included in the source documentation at the study site. Clinically relevant findings that are present prior to signing informed consent must be recorded on the appropriate eCRF that captures medical history. Significant findings made after signing the informed consent which meet the definition of an AE must be recorded as an AE.
Vital signs	Vital signs include BP and pulse measurements. After the subject has been sitting for five minutes, with back supported and both feet placed on the floor, systolic and diastolic blood pressure will be measured three times using an automated validated device, e.g. OMRON, with an appropriately sized cuff. The repeat sitting measurements will be made at 1 - 2 minute intervals and the mean of the three measurements will be used. In case the cuff sizes available are not large enough for the subject's arm circumference, a sphygmomanometer with an appropriately sized cuff may be used.  Clinically notable vital signs are defined in Section 16.1 .
Height and weight	Height in centimeters (cm) and body weight (to the nearest 0.1 kilogram (kg) in indoor clothing, but without shoes) will be measured.

As per [Section 4.6](#), during a Public Health emergency as declared by Local or Regional authorities, i.e., pandemic, epidemic or natural disaster, that limits or prevents on-site study visits, regular phone or virtual calls can occur (every 4 weeks or more frequently if needed) for safety monitoring and discussion of the participant's health status until it is safe for the participant to visit the site again.

#### **8.4.1 Laboratory evaluations**

A central laboratory will be used for analysis of all specimens detailed in this section ([Table 8-10](#)) unless noted otherwise. Details on the collections, shipment of samples and reporting of results by the central laboratory are provided to investigators in the laboratory manual.

If participants cannot visit the site for protocol specified safety lab assessments (per [Section 4.6](#)), an alternative lab (local) collection may be used.

Clinically notable laboratory findings are defined in [Appendix 1](#).

Clinically significant abnormalities must be recorded on the relevant section of the eCRFs capturing medical history/current medical conditions/AEs.

**Table 8-10      Laboratory assessments**

Test Category	Test Name
Hematology	Hematocrit, Hemoglobin [only in case of clinically significant anemia, the following parameters will be assessed: Mean Corpuscular Hemoglobin (MCH), Mean Corpuscular Hemoglobin Concentration (MCHC), Mean Corpuscular Volume (MCV)], Platelets, Red blood cells (RBC), White blood cells (WBC) and Differential (Basophils, Eosinophils, Lymphocytes, Monocytes, Neutrophils, Bands)
Chemistry	Albumin, Alkaline phosphatase (ALP), ALT, AST, Gamma-glutamyl-transferase (GGT), Lactate dehydrogenase (LDH), Calcium, Magnesium, Phosphorus, Chloride, Sodium, Potassium, Creatine Kinase (CK), Creatinine, total Bilirubin (in case of clinically significant elevation: direct Bilirubin and indirect Bilirubin will be assessed), [Canada only: eGFR] Only at baseline (day 1), Week 28 and 52: total Cholesterol, Low density Lipoprotein (LDL), High density Lipoprotein (HDL), Total Protein, Triglycerides, Blood Urea Nitrogen (BUN) or Urea, Uric Acid, Amylase, Lipase, Glucose (fasting) Only at baseline and when deemed necessary by the investigator: C-reactive Protein (CRP)
Urinalysis	Done on site: Macroscopic Panel (Dipstick) (Color, Bilirubin, Blood, Glucose, Ketones, Leukocytes esterase, Nitrite, pH, Protein, Specific Gravity, Urobilinogen)
Coagulation	Prothrombin time (PT)/International normalized ratio (INR), Activated partial thromboplastin time (APTT)
Additional tests	IgE, [REDACTED] serum pregnancy test (for WoCBP)
Pregnancy Test	Urine pregnancy test for WoCBP

#### **8.4.2      Electrocardiogram (ECG)**

ECGs will be analyzed centrally and performed with ECG machines supplied by the central provider. Standard 12-lead ECGs (single readings) must be recorded after 10 minutes rest in the supine position according to the ECG investigator manual at the timepoints indicated in [Table 8-1](#). The preferred sequence of cardiovascular data collection during study visits is ECG collection first, followed by vital signs, and blood sampling. The Fridericia QT correction formula (QTcF) should be used for clinical decisions.

For any ECGs with treatment emergent abnormalities, two additional ECGs must be performed to confirm the abnormal finding and copies forwarded to the central ECG laboratory for assessment. A monitoring or review process should be in place for clinically significant ECG findings throughout the study and especially at baseline before administration of study treatment.

In the event that a clinically significant ECG abnormality is identified at the site (e.g. severe arrhythmia, conduction abnormality of QTcF > 500 ms or QTcF prolongation > 60 ms), a copy of the assessment is sent to the core laboratory for expedited review if applicable, and the ECG is repeated (and a copy sent to the core laboratory) to confirm the diagnosis. If the subject is hemodynamically compromised, the investigator or a medically qualified person must initiate appropriate safety procedures without delay (for example cardioversion).

Clinically significant abnormalities must be recorded on the eCRF as either medical history/current medical conditions or AEs as appropriate.

#### **8.4.3      Pregnancy**

All pre-menopausal women who are not surgically sterile will have pregnancy testing at day 1 of the treatment period (on serum), and every 4 weeks thereafter (compare [Table 8-1](#)) on urine (tests may be performed at home if there is no scheduled study visit). To obtain home-test results, sites must contact subjects. Any positive or undetermined urine test needs to be confirmed by a serum pregnancy test. If positive, the subject must be discontinued from study treatment.

Additional pregnancy testing might be performed if requested by local requirements.

If participants cannot visit the site to have pregnancy tests as scheduled at site, urine pregnancy test kits may be used. Relevant participants can perform the urine pregnancy test at home and report the result to the site. It is important that participants are instructed to perform the urine pregnancy test first, and only if the test result is negative are they to proceed with administration of the study treatment. A communication process should be established with the participant so that the site is informed and can verify the pregnancy test results (e.g., following country-specific measures).

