## 5.2 Exclusion criteria

1. Use of other investigational drugs within 5 half-lives of enrollment, or within 30 days (for small molecules) prior to enrollment or until the expected pharmacodynamic (PD) effect has returned to baseline (for biologics), whichever is longer; or longer if required by local regulations.
2. History of hypersensitivity to any of the study drugs or its excipients or to drugs of similar chemical classes.
3. Subjects having a clearly defined, predominant or sole trigger of their chronic urticaria (chronic inducible urticaria) including urticaria factitia (symptomatic dermographism), cold-, heat-, solar-, pressure-, delayed pressure-, aquagenic-, cholinergic-, or contact urticaria
4. Other diseases with symptoms of urticaria or angioedema, including but not limited to urticaria vasculitis, urticaria pigmentosa, erythema multiforme, mastocytosis, hereditary urticaria, or acquired/drug-induced urticaria
5. Any other skin disease associated with chronic itching that might influence in the investigators opinion the study evaluations and results, e.g. atopic dermatitis, bullous pemphigoid, dermatitis herpetiformis, senile pruritus or psoriasis
- 6a History or current diagnosis of ECG abnormalities indicating significant risk of safety for subjects participating in the study such as:
  - Concomitant clinically significant cardiac arrhythmias, e.g. sustained ventricular tachycardia, and clinically significant second or third degree AV block without a pacemaker
  - History of familial long QT syndrome or known family history of Torsades de Pointes
  - Resting heart rate (as measured by 12 lead ECG)  $< 50$  bpm at day 1 of treatment
  - Resting QTcF  $\geq 450$  msec (male) or  $\geq 460$  msec (female) at day 1 of the treatment period or inability to determine the QTcF interval
  - Use of agents known to prolong the QT interval unless they can be permanently discontinued for the duration of study
7. Patients/subjects taking medications prohibited by the protocol  
(see [Section 6.2.2, Table 6-2](#))

8. History of malignancy of any organ system (other than localized basal cell carcinoma of the skin or in situ cervical cancer), treated or untreated, within the past 5 years, regardless of whether there is evidence of local recurrence or metastases.
9. Pregnant or nursing (lactating) women

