10. Women of child-bearing potential, defined as all women physiologically capable of becoming pregnant, **unless** they are using highly effective methods of contraception during dosing and for 7 days after stopping study medication. Highly effective contraception methods include:
  - Total abstinence (when this is in line with the preferred and usual lifestyle of the subject). Periodic abstinence (e.g., calendar, ovulation, symptothermal, post-ovulation methods) and withdrawal are not acceptable methods of contraception
  - Female sterilization (have had surgical bilateral oophorectomy with or without hysterectomy) total hysterectomy or tubal ligation at least six weeks before taking investigational drug. In case of oophorectomy alone, only when the reproductive status of the woman has been confirmed by follow up hormone level assessment
  - Male sterilization (at least 6 months prior to screening). For female subjects on the study, the vasectomized male partner should be the sole partner for that subject
  - Use of oral, (estrogen and progesterone), injected or implanted hormonal methods of contraception or placement of an intrauterine device (IUD) or intrauterine system (IUS) or other forms of hormonal contraception that have comparable efficacy (failure rate <1%), for example hormone vaginal ring or transdermal hormone contraception

In case of use of oral contraception women should have been stable on the same pill for a minimum of 3 months before taking investigational drug.

Women are considered post-menopausal and not of child bearing potential if they have had 12 months of natural (spontaneous) amenorrhea with an appropriate clinical profile (e.g. age appropriate, history of vasomotor symptoms) or have had surgical bilateral oophorectomy (with or without hysterectomy), total hysterectomy or tubal ligation at least six weeks ago. In the case of oophorectomy alone, only when the reproductive status of the woman has been confirmed by follow up hormone level assessment is she considered not of child bearing potential.

11. Exclusion criterion had become irrelevant.
12. Major surgery within 8 weeks prior to enrollment or surgery planned prior to end of the treatment period.
13. History of live attenuated vaccine within 6 weeks prior to enrollment or requirement to receive these vaccinations at any time during study drug treatment

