14. Evidence of clinically significant cardiac, neurologic, psychiatric, pulmonary, renal, hepatic, endocrine, metabolic, hematological disorders or gastrointestinal disease that, in the investigator's opinion, would compromise the safety of the participant, interfere with the interpretation of the study results or otherwise preclude participant participation.
15. Uncontrolled disease states, such as asthma, or inflammatory bowel disease, where flares are commonly treated with oral or parenteral corticosteroids
16. Hematology parameters at last visit before Day 1 of the Treatment period (either last available value from CLOU064A2201 or most recent value taken during observational period):

- Hemoglobin: < 10 g/dl
- Platelets: < 100 000/mm^3
- White blood cells: < 3 000/mm^3
- Neutrophils: < 1 500/mm^3

17. Significant bleeding risk or coagulation disorders

18. History of gastrointestinal bleeding, e.g. in association with use of Nonsteroidal Anti-Inflammatory Drug (NSAID)

19. Requirement for anti-platelet or anticoagulant medication (for example, warfarin, or clopidogrel or Novel Oral Anti-Coagulant - NOAC) other than acetylsalicylic acid (up to 100 mg/d)

20. History or presence of thrombotic or thromboembolic event, or increased risk for thrombotic or thromboembolic event

21. History or current treatment for hepatic disease including but not limited to acute or chronic hepatitis, cirrhosis or hepatic failure or Aspartate Aminotransferase (AST)/Alanine Aminotransferase (ALT) levels of more than 1.5 x upper limit of normal (ULN) at last visit before Day 1 of the Treatment period (either last available value from CLOU064A2201 or most recent value taken during observational period)

22. History of renal disease or creatinine level above 1.5x ULN at last visit before Day 1 of the Treatment period (either last available value from CLOU064A2201 or most recent value taken during observational period)

[**Canada only:** History of renal disease, creatinine level above 1.5x ULN or eGFR <45ml/min (using the Cockcroft-Gault equation) at last visit before Day 1 of the Treatment period (either last available value from CLOU064A2201 or most recent value taken during observational period)]

23. Known or suspected history of an ongoing, chronic or recurrent infectious disease including but not limited to opportunistic infections (e.g. tuberculosis, atypical mycobacterioses, listeriosis or aspergillosis), HIV, Hepatitis B/C

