**Table 8-1 Assessment Schedule, Treatment period and Follow-up period**

Period	Open Label Treatment										Treatment free follow-up			Unscheduled visit
Visit	Screening								EoTV 				Study Completion Visit 	
Days	1	29	57	85	113	141	197	281	365 (or early termination)	393 	421  	449  	393-477	NA
Weeks	1	4	8	12	16	20	28	40	52	56	60	64	56-68	NA
Informed consent	X													
Prior study participation	X													
Inclusion / Exclusion criteria	X													
Demography	X													
Physical Examination 	S 	S	S	S	S	S	S	S	S	S			S	S
Vital Signs	X 	X	X	X	X	X	X	X	X	X			X	X
Body Weight	X 						X		X				X	X
Electrocardiogram (ECG)	X 	X	X	X		X	X	X	X				X	X
Concomitant medications	X 	X	X	X	X	X	X	X	X	X	X	X	X	X
Adverse Events	X 	X	X	X	X	X	X	X	X	X	X	X	X	X
Drug dispensation	X	X	X	X	X	X	X	X						X
IRT transaction	X	X	X	X	X	X	X	X	X					X

Period	Open Label Treatment									Treatment free follow-up			Unscheduled visit	
Visit	Screening								EoTV 				Study Completion Visit 	
Days	1	29	57	85	113	141	197	281	365 (or early termination)	393 	421  ☎	449  ☎	393-477	NA
Weeks	1	4	8	12	16	20	28	40	52	56	60	64	56-68	NA
Subjects' eDiary review  - UPDD (incl. UAS)	S 	S	S	S	S	S	S	S	S	S	S	S	S	S
Study drug compliance Assessment		S	S	S	S	S	S	S	S					S
Urinalysis	X 	X	X	X	X	X	X	X	X	X			X	X
Clinical Chemistry	X 	X	X	X	X	X	X	X	X	X			X	X
Hematology	X 	X	X	X	X	X	X	X	X	X			X	X
Coagulation Panel	X 						X		X				X	X
Total IgE				X		X		X					X	X
Pregnancy Test (serum) 	X													
Pregnancy test (urine) 		S	S	S	S	S	S	S	S	S			S	S

Period	Open Label Treatment									Treatment free follow-up				Unscheduled visit
Visit	Screening								EoTV 				Study Completion Visit 	
Days	1	29	57	85	113	141	197	281	365 (or early termination)	393 	421  ☎	449  ☎	393-477	NA
Weeks	1	4	8	12	16	20	28	40	52	56	60	64	56-68	NA
Check eligibility for entering extended Follow-up (up to 16 weeks)									S					
Disposition (end of treatment and study disposition)	X													

X: recorded in the eCRF; S: recorded in the source documents only

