**Table 8-2 Assessment Schedule, Observational period**

Visit	Screening			EoOP 	Unscheduled visit
Days	1	29 	57 	8-85	NA
Weeks	1	4	8	1-12	NA
Informed consent	X				
Prior study participation	X				
Inclusion / Exclusion criteria	X				
Demography	X				
Short Physical Examination	S			S	S
Adverse Events	X 	X	X	X	X
Concomitant medications	X 	X	X	X	X
Subjects' eDiary review  : - UPDD (incl. UAS)	S 	S	S	S	S
Clinical Chemistry		X	X	X	X
Hematology		X	X	X	X
Total IgE				X	X
Study disposition			X		

X: recorded in the eCRF; S: recorded in the source documents only

 UPDD: Urticaria Patient Daily Diary; UAS: Urticaria Activity Score; [REDACTED]

 Only assess if day 1 of observational period is more than 1 week after Week 16 of core study

 If CSU relapse is detected at the visit: please directly perform an EoOP visit instead of the preplanned day 29 or day 57 visit

 EoOP: End of Observational Period can be directly after a CSU relapse (defined as UAS7≥16) was detected (either during a scheduled or an unscheduled visit); in case, EoOP and day 1 of the treatment period are at the same day, assessments only need to be done once.  
[REDACTED]

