## **8.1 Screening**

At day 1 of the treatment period and at day 1 of the observational period (if applicable), all inclusion and exclusion criteria will be checked. For all laboratory assessments, the results from the last visit before Day 1 of the treatment period (either the last available value from CLOU064A2201 or most recent value taken during observational period) will be used.

Eligibility for this study will be assessed at Week 12 and Week 16 of the preceding core study CLOU064A2201. Subjects who are not eligible for enrollment into this extension study at Week 12 for any reason will not be assigned to a subject number for this extension study but will enter the follow-up period of CLOU064A2201. Re-screening of subjects who are not eligible at Week 16 is not permitted.

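### The Day 1 serum pregnancy test is not tied to the first dose; an on-site urine test before dispensation would close the gap cheaply

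*Protocol*

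**What the plan says.** **Entry requirement.** Protocol 5.2, exclusion 9, bars "Pregnant or nursing (lactating) women". Under 8.1, at Day 1 of the treatment period, and of the observational period where there is one, "all inclusion and exclusion criteria will be checked".

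**Test.** Protocol 8.4.3 says "All pre-menopausal women who are not surgically sterile will have pregnancy testing at day 1 of the treatment period (on serum", followed by urine tests every four weeks. In Table 8-1 the row "Pregnancy Test (serum" is marked at Day 1 only, for women of childbearing potential. The urine row starts at Week 4 (Day 29). Drug dispensation is marked at Day 1 too.

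**Laboratory.** Table 8-10 lists the serum pregnancy test, and 8.4.1 sends the specimens in that table to a central laboratory unless noted otherwise. Only the urine dipstick panel is noted as done on site.

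**Which results count.** Section 8.1 adds: "For all laboratory assessments, the results from the last visit before Day 1 of the treatment period" are the ones to be used. Exclusion 16 repeats this ("Hematology parameters at last visit before Day 1 of the Treatment period"), and exclusions 21 and 22 do the same for liver enzymes and creatinine.

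**Observational period.** Table 8-2 shows chemistry and hematology but no pregnancy test. Its footnote 5 adds that where "EoOP and day 1 of the treatment period are at the same day, assessments only need to be done once".

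**Contraception.** Exclusion 10 excludes women of childbearing potential unless "they are using highly effective methods of contraception during dosing and for 7 days after stopping study medication".

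**Test-before-dose rule.** Section 8.4.3 contains one. It applies to urine tests done at home when the participant cannot come to the site.

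**The concern.** The protocol requires non-pregnancy at entry and schedules a test for it. But the only visible pre-treatment test in the extension is drawn at the visit where drug is handed out, and its result comes from elsewhere. Nothing visible orders the two events, so a site that follows the schedule to the letter may dispense, and the subject may start, before the result is known. The stated consequence of a confirmed positive test in 8.4.3 is that study treatment is discontinued, which acts after exposure has begun.

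Sections 4.5 and 7 describe unknown risks to the fetus, and 9.1.1 makes pregnancy a mandatory reason to stop treatment. What is at stake is an avoidable early exposure that a test read at the same visit could often prevent. LOU064's own reproductive findings are redacted, so nothing can be said about how large the harm would be.

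**Working it through.** The plan gives no figure to reproduce. The check is a comparison of texts plus simple timing.

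**1. Order of events at treatment Day 1**

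| Event | Source | Timing |
|---|---|---|
| Eligibility check, including exclusion 9 | 8.1, 5.2 | Day 1 |
| Serum pregnancy sample drawn | 8.4.3, Table 8-1 | Day 1 |
| Serum result available | 8.4.1, Table 8-10 | Day 1 plus central-laboratory turnaround (not stated) |
| Drug dispensed | Table 8-1 | Day 1 |
| First dose | no visible rule linking it to the result | Day 1 or later |

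The third row can fall after the fifth, and no visible sentence prevents it.

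**2. Size of the window.** Possible doses before the result = turnaround in days × 2 doses per day (100 mg twice daily, 6.1.3). The turnaround is not in the documents. Assuming 1 to 7 days:

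- 1 day: 1 × 2 = 2 doses
- 7 days: 7 × 2 = 14 doses

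This range only illustrates the assumption. If the site waits for the result, the number is 0.

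**3. Two intervals that do not measure the window**

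- Observational period: Day 85 − Day 1 = 84 days (12 weeks) with no visible pregnancy test. No LOU064 is given then, so these are not days of exposure. They matter only because any earlier test result would have to come from the core study and could be that old by treatment Day 1.
- Day 1 to the next scheduled pregnancy test: Day 29 − Day 1 = 28 days. This is not the window either, because the Day 1 serum result would normally be back first and a positive one would stop treatment.

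**4. Contraception before treatment Day 1.** Core Week 16 − core Week 12 = 4 weeks = 28 days off drug, taking the last core dose to be at Week 12, the end of core treatment. Since 28 > 7, the period of dosing plus 7 days has passed before observation begins. Exclusion 10 therefore does not clearly require contraception during observation, although it is checked again at treatment Day 1.

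**5. Who could still benefit.** Amendment 2 (05-Apr-2021) reports about 227 rolled over. Section 5 expects about 250, with 308 as the theoretical maximum.

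- 250 − 227 = about 23 still to enter, both sexes
- 308 − 227 = about 81 at the very most

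Some of the 227 may still have been in observation at that date. From 05-Apr-2021 to Amendment 3 (08-Sep-2021) is 156 days, longer than the 84-day observational period, so few if any of them would still have been waiting to start by then.

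**The case against.** **The test is there.** The Day 1 visit is labelled as screening, exclusion 9 is checked at it, and a serum test is scheduled. Many Day 1 assessments are waived when Day 1 falls within a week of rollover (footnote 8 to Table 8-1); the serum pregnancy test is not. The natural reading is that its result serves exclusion 9. This stands. A reader might infer that the protocol does not verify pregnancy at entry at all, and that would be wrong: what is missing is the sentence that orders result and dose.

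**Section 8.1 need not displace the Day 1 result.** Taken literally, its rule about the last visit before Day 1 would make the Day 1 serum result irrelevant to eligibility. But only exclusions 16, 21 and 22 repeat that rule. Exclusion 9 does not, and 8.4.3 is the more specific text. The literal reading is not the better one, so the point does not rest on it.

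**Other safeguards.** A site may wait for the result, 8.4.3 foresees extra tests under local requirements, and 8.1.1 foresees subjects who never start treatment. SAP 2.1.1.2 defines enrollment and first dose separately, and SAP Table 5-1 has a code for subjects who took no drug. Exclusion 10 also sets lead times: three months on a stable pill, six weeks after female sterilization, and six months before screening for a vasectomized partner. These lower the risk. None of them requires a negative result before the first dose.

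**Comparison with ECGs.** Section 8.4.2 asks for a review process before baseline dosing, but it sets no hold on the dose, so it adds little.

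**What cannot be seen.** The core-study test schedule and the laboratory manual are not available. Gaps in the footnote numbering suggest redacted rows in Tables 8-1 and 8-2. The text of 8.4.3 shows no redaction and gives the schedule as serum at Day 1, then urine. The claim is still limited to what is visible.

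**Conclusion.** The point holds as a gap in sequencing. A serum test is scheduled for every woman of childbearing potential at treatment Day 1, but the visible text allows a first dose before its result is known. The protocol already applies a negative-first rule to home testing and has no equivalent for the first on-site dose.

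The conclusion rests on three conditions: the serum sample goes to the central laboratory as 8.4.1 provides by default, no redacted text holds the first dose, and dosing may begin once drug is dispensed. Dispensing alone is not exposure. The documents do not say that any woman is dosed before her result, and a reader should not infer that this will happen. Nor should the 12 weeks without a visible test, or the four weeks to the next one, be read as exposure time.

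The size of the risk is unknown, and the number of women who could still benefit is small by the time of the current version. This is a cheap safety improvement. It does not affect the analysis or the validity of the results.

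**What to change.** 1. In Table 8-1, add an on-site urine pregnancy test at Day 1 for women of childbearing potential, before drug dispensation. Keep the serum test, since urine can miss a very early pregnancy.
2. In 8.4.3, state that the first dose is given only after a negative Day 1 result (urine, or serum if already available), and that a positive or undetermined urine result holds dispensation until the serum result is known.
3. Optionally, state in 8.1 that the Day 1 result is the one that serves exclusion 9.

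With the first two changes, a result is known at the same visit as dispensation on every entry route.

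**Cost.** One urine kit per woman, with urine tests already in use from Week 4, and an occasional short delay to the first dose. The change also needs a written protocol amendment, with ethics committee approval and health authority approval where required (14.1). With few women left to enter, it would sensibly be combined with another amendment, or carried into the next study's protocol.
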